### **Stages**

- Stage 0: This is the mildest form of ROP. It is immature retinal vasculature. No clear demarcation of vascularized and nonvascularized retina is present. Only a suggestion of the border is noted on examination.
- Stage 1: A fine, thin demarcation line between the vascular and avascular region is present. This line has no height and no thickness.
- Stage 2: A broad, thick ridge clearly separates the vascular from the avascular retina.
- Stage 3: The extraretinal fibrovascular proliferation (neovascularization) may be present on the ridge, on the posterior surface of the ridge or anteriorly toward the vitreous cavity. The neovascularization gives the ridge a velvety appearance, a ragged border.
- Stage 4: This stage is a subtotal retinal detachment beginning at the ridge. The retina is pulled anteriorly into the vitreous by the fibrovascular ridge.
- Stage 5: This stage is a total retinal detachment in the shape of a funnel.

**Bronchopulmonary Dysplasia**

- Clinical signs and symptoms consistent with neonatal lung disease
- The subject meets specific NICHD diagnostic criteria specified in the table below.

National Institute of Child Health and Human Development Criteria for Diagnosis of Bronchopulmonary Dysplasia (BPD)*	
< 32 Wk Gestational Age†	Diagnosis†
Need for < 30% O 2 at 36 wk PMA or discharge, whichever comes first	Mild to Moderate BPD
Need for ≥ 30% O 2 , positive pressure or both at 36 wk PMA or discharge, whichever comes first	Severe BPD

\*NOTE: These criteria are in addition to the baseline requirement of > 21% O2 for at least 28 days.  
†Assessed at 36 wk postmenstrual age (PMA).

**Intraventricular Hemorrhage**

Hemorrhage noted on cranial ultrasonography:

- Grade I - Hemorrhage of subependymal region and/or germinal matrix
- Grade II - Subependymal hemorrhage with extension into lateral ventricles without ventricular enlargement
- Grade III - Subependymal hemorrhage with extension into lateral ventricles with ventricular enlargement
- Grade IV - Intraparenchymal hemorrhage

### APPENDIX C – ANTIBIOTIC SUSCEPTIBILITY

In the event of an infection due to [REDACTED] STP6 or [REDACTED] STP11, the minimum inhibitory concentrations (MICs) for 20 commonly used antibiotics are presented in the [REDACTED]

[REDACTED]	[REDACTED]	[REDACTED]
[REDACTED]	[REDACTED]	[REDACTED]

**APPENDIX D – ESTIMATED FETAL WEIGHT PERCENTILE CHART**

**Girls**

AGA (10-90th %tile) Measurements at Birth

Gestation*	Weight (g)	Head (cm)
23	477 – 687	19.5 – 22.2
24	524 – 772	20.3 – 23.2
25	584 – 885	21.1 – 24.1
26	645 – 1,004	22 – 25.1
27	719 – 1,147	22.8 – 26.2
28	807 – 1,310	23.7 – 27.3
29	915 – 1,489	24.6 – 28.4
30	1,052 – 1,693	25.6 – 29.4
31	1,196 – 1,897	26.5 – 30.3
32	1,352 – 2,116	27.4 – 31.2
33	1,545 – 2,379	28.3 – 32.1
34	1,730 – 2,661	29.1 – 33.1
35	1,869 – 2,985	29.8 – 34
36	2,028 – 3,339	30.5 – 34.8
37	2,260 – 3,651	31.1 – 35.4
38	2,526 – 3,847	31.7 – 35.7
39	2,724 – 3,973	32 – 36
40	2,855 – 4,070	32.3 – 36.1
41	2,933 – 4,142	32.6 – 36.3

\*Choose gestation based on weeks completed.  
 (25/2 = 25 weeks, 25/6 = 25 weeks)

Weight	Head	Classification
10-90%	10-90%	AGA
<10%	10-90%	SGA/Head-Spared
<10%	<10%	SGA/Symmetric
>90%	>90%	LGA

# Boys

## AGA (10-90th %tile) Measurements at Birth

Gestation*	Weight (g)	Head (cm)
23	509 – 727	20 – 22.7
24	561 – 813	20.8 – 23.6
25	626 – 926	21.7 – 24.6
26	704 – 1,065	22.5 – 25.7
27	789 – 1,218	23.5 – 26.8
28	884 – 1,385	24.3 – 27.9
29	988 – 1,560	25.2 – 28.8
30	1114 – 1,761	26.1 – 29.8
31	1267 – 1,984	27 – 30.8
32	1433 – 2,218	27.8 – 31.8
33	1625 – 2,488	28.7 – 32.7
34	1810 – 2,763	29.5 – 33.6
35	1980 – 3,084	30.3 – 34.5
36	2170 – 3,432	31 – 35.3
37	2401 – 3,736	31.7 – 36
38	2652 – 3,986	32.2 – 36.4
39	2833 – 4,129	32.5 – 36.6
40	2950 – 4,232	32.8 – 36.8
41	3039 – 4,319	33 - 37

\*Choose gestation based on weeks completed.  
(25/2 = 25 weeks, 25/6 = 25 weeks)

Weight	Head	Classification
10-90%	10-90%	AGA
<10%	10-90%	SGA/Head-Spared
<10%	<10%	SGA/Symmetric
>90%	>90%	LGA

## APPENDIX E – REVIEW OF INFECTIONS SUSPECTED TO INVOLVE STP206 ORGANISMS

1 LIST OF ABBREVIATIONS AND DEFINITIONS OF TERMS

Table 1: Abbreviations and Definitions of Terms

Abbreviation	Term
AE	Adverse event
AGA	Appropriate for gestational age
BP	Blood pressure
BPD	Bronchopulmonary Dysplasia
BW	Birth Weight
CI	Confidence interval
CRA	Clinical Research Associate
CRF	Case report form
DSMC	Data safety and monitoring committee
ELBW	Extremely low birth weight
FDA	U.S. Food and Drug Administration
g	Gram
HR	Heart rate
IRB	Institutional review board
IVH	Intraventricular Hemorrhage
ITT	Intent-to-treat
LBP	Live Biotherapeutic Product
LBW	Low birth weight
LGA	Large for gestational age
MedDRA	Medical dictionary for regulatory activities
N	Number of subjects
NEC	Necrotizing Enterocolitis
PK	Pharmacokinetic
ROP	Retinopathy of prematurity
RR	Respiratory rate
SAS®	Statistical analysis software
SAE	Serious Adverse Event
SD	Standard deviation
SGA	Small for gestational age
SOC	System organ class
TEAE	Treatment-Emergent Adverse Event
Temp	Temperature

Abbreviation	Term
VLBW	Very low birth weight
WHO	World Health Organization

2 INTRODUCTION

Leadiant Biosciences, Inc. (Leadiant) is developing STP206, a Live Biotherapeutic Product (LBP), for the prevention of Necrotizing Enterocolitis (NEC) in premature very low birth weight (VLBW) (<1500 g) and extremely low birth weight (ELBW) (<1000 g) infants.

2.1 Disease Background

Necrotizing Enterocolitis (NEC) is the most common serious acquired disease of the gastrointestinal tract in preterm infants¹ with the majority of NEC occurring in infants with birth weight (BW) below 1500 g.² NEC is characterized by signs of abdominal distension, intra-abdominal inflammation, and radiologic presence of pneumatosis intestinalis and/or portal venous air or free air indicating perforation.

In 2008, there were approximately 347,209 premature babies weighing less than 2500 g born in the United States, with approximately 61,773 of these babies weighing less than 1500 g at birth³. These VLBW babies are at the highest risk for developing NEC. NEC has been reported to occur in approximately 10% of VLBW infants², although the incidence varies among countries and neonatal centers. The mortality rate of VLBW infants with NEC is approximately 20%^{4, 5}. In addition to the mortality rates, infants with NEC often have other complications and require other interventions and extended hospitalizations⁶. Data from the National Institute of Child Health and Human Development Network (NICHD) suggest an increase in neurodevelopmental impairment rates among infants with NEC and sepsis⁷.

Over the past 30 years, several interventions to decrease the incidence of NEC in VLBW infants have been attempted, including feeding manipulation, prophylactic antibiotics, and immunoglobulins; however, the mortality rate has remained unchanged.

2.2 Description of Investigational Product

STP206 Live Biotherapeutic contains [REDACTED] STP6 [REDACTED] and [REDACTED] STP11. The product is manufactured by [REDACTED] for Leadiant under current good manufacturing practices (cGMP) regulations for pharmaceutical grade biologic drugs.

2.2.1 Probiotics for the Prevention of NEC

[figure not shown]
There have been no clinical studies conducted to date with STP206 for the prevention of NEC in Neonates other than the current STP206-002 study.

[REDACTED]

2.3 Target Population and Study Rationale

The target population for intended clinical use of STP206 is premature VLBW infants (1500 to 1001 g) and ELBW infants (1000 to 500 g) who are at risk of developing NEC.

The hypothesis is, therefore, that influencing the intestinal flora by the administration of probiotics can provide a balance between beneficial and pathogenic bacteria, modulate the pro-inflammatory response, and enhance intestinal maturation; thus, possibly reducing the incidence of NEC. This hypothesis is supported by the clinical trials (see Section 5.3.2.2 of the protocol) conducted with probiotics to date. These published clinical studies conducted in neonates  suggest that supplementation of VLBW infants with STP206 may have clinical use in the prevention of NEC.

3 STUDY OBJECTIVES

The study will be a sequential dose escalation study to examine the safety, tolerability, and preliminary NEC-preventative efficacy of two dose levels of STP206 in premature VLBW and ELBW neonates.

3.1 Sequential Dose Escalating Study

3.1.1 Primary Objectives

To assess the safety and tolerability of once-daily dosing of two dose levels of STP206 versus control in four different BW strata in premature neonates

3.1.1.1 Secondary Objectives

The secondary objectives of the study are to:

- Assess the fecal shedding after daily dosing of each component of STP206 throughout the dosing phase.
- Describe the incidence of NEC in STP206-treated subjects compared to control subjects.
- Describe the incidence of clinical events (sepsis/bacteremia, feeding intolerance, morbidity/complications of prematurity) in STP206-treated subjects compared to control subjects.
- Describe the progression of standard neonatal growth parameters in STP206-treated subjects compared to control subjects.

4 STUDY DESIGN

4.1 General Design

Protocol STP206-002 is designed as a multi-center, randomized, double-blind, and placebo-controlled study with dose escalation to examine the safety, tolerability, and preliminary NEC-preventative efficacy of two doses of STP206 versus control in four sequentially decreasing BW strata.

[figure not shown]
All neonates enrolled in the study will be randomized and will receive daily doses of blinded study treatment (STP206 or control) for between 2 and 11 weeks, through 34 weeks post-conceptual age or hospital discharge, whichever comes first. All neonates enrolled in the study will be placed under Universal Precautions and all study personnel with subject contact are trained in appropriate NICU infection control practices.

- The doses of STP206 to be administered are:
 - Low dose STP206: approximately 1 billion (1×10^9) CFU of [REDACTED] and approximately 100 million (1×10^8) CFU of [REDACTED] (total of 1.1 billion CFU)
 - High dose STP206: approximately 9 billion (9×10^9) CFU of [REDACTED] and approximately 900 million (9×10^8) CFU of [REDACTED] (total of 9.9 billion CFU)
- Neonates will be stratified into the following four birth weights: 2000-1501 g, 1500 to 1000 g, 999 to 750 g and 749 to 500 g.
- Within each BW strata, subjects will be randomized to the STP206 low dose or control group followed by the STP206 high dose or control group, resulting in the following eight study groups:
 - Study Group 1a – BW 2000 to 1501 g and Low dose STP206 versus control

- Study Group 1b – BW 2000 to 1501 g and High dose STP206 versus control
- Study Group 2a – BW 1500 to 1000 g and Low dose STP206 versus control
- Study Group 2b – BW 1500 to 1000 g and High dose STP206 versus control
- Study Group 3a – BW 999 to 750 g and Low dose STP206 versus control
- Study Group 3b – BW 999 to 750 g and High dose STP206 versus control
- Study Group 4a – BW 749 to 500 g and Low dose STP206 versus control
- Study Group 4b – BW 749 to 500 g and High dose STP206 versus control
- Each BW strata/STP206 dose group will consist of approximately 12 subjects.
- Within each BW strata/STP206 dose group, subjects will be randomized in a 2:1 ratio to either the STP206 or control group.
- Enrollment of neonates into study groups will occur sequentially. Enrollment into the high dose group within a BW stratum will not proceed until after the safety data from the low dose group is reviewed by the study independent Data Safety Monitoring Committee (DSMC). Similarly, enrollment into the next lower BW stratum will not proceed until the safety data from the high dose group of the prior weight stratum is reviewed by the study independent DSMC. If, at any point during the study the DSMC determines that the high dose of STP206 is not safe and well tolerated, weight de-escalation will continue with the low dose of STP206.

The sequencing of treatment groups of the study is shown in Figure 1. Enrollment will begin with neonates weighing 2000 - 1500 g at the low dose of STP206 (Group 1a). Safety data through the last dose of blinded study treatment will be evaluated by the DSMC (see Protocol Section 7.7). Subsequent cohorts will not open for enrollment before the data from the previous cohort has been reviewed by the DSMC. If the safety data review conducted by the DSMC determines there are no safety concerns, study groups will open sequentially as illustrated in the figure below.

Figure 1 – Treatment Group Sequence

Following completion of blinded study treatment dosing, neonates will be evaluated at 1 week, 1 month, 3 months, and 6 months for safety and growth assessments.

4.2 Discussion of Study Design

Not applicable.

4.3 Method of Assignment of Subjects to Treatment Groups

Neonates enrolled into the study will be randomized to receive either STP206 or control in a 2:1 ratio based upon a pre-prepared, computer generated, centralized randomization schedule. To assure a balance in BW among treatment groups, randomization will be stratified by BW in four strata: 2000-1501g, 1500 to 1000 g, 999 to 750 g and 749 to 500 g.

4.4 Blinding

All staff performing study assessments will be blinded to the identity of the treatment assignment to which the infant has been randomized in an effort to minimize bias in study assessments. Fecal shedding results will not be shared with the study sites during the course of the study as these results may potentially unblind study staff to the identity of treatment.

As study treatment is supplied in open-label fashion, the study will require unblinded site personnel to randomize subjects and prepare study treatments for administration, the study will use a third party (e.g., pharmacist or other designated site personnel who has no role in screening, enrolling or qualifying study subjects) to minimize bias in study conduct.

As there may be a visual difference between STP206 and control treatments (clear vs. white, respectively) an opaque syringe will be used to administer the blinded study treatment.

Only the staff who assist the process of preparing randomization assignments/labels for independent pharmacist, the designated unblinded site monitors, and the statistician who

assists preparing data for the independent Data Safety Monitoring Committee (DSMC) will be unblinded to the study.

4.5 Determination of Sample Size

The sample size of this study was not statistically determined.

5 CHANGES IN THE CONDUCT OF THE STUDY OR PLANNED ANALYSES

5.1 Changes in the Conduct of the Study

Protocol version 2.0, Amendment 1, dated 06JAN2014, revised sections of the protocol to provide clarification regarding procedures/evaluations to be done. This Amendment was implemented prior to the start of subject enrollment.

Protocol version 3.0, Amendment 2, dated 08JUL2018, revised protocol to remove Part B of the study as well as the Month 18 Follow-up Visit. Data beyond Month 6 post dosing will only be presented in listings unless specifically detailed in this SAP.

5.2 Changes from the Analyses Planned in the Protocol

The definition of the Intent-to-treat analysis population was changed in this SAP to include all subjects that are randomized regardless of dosing status.

5.3 Changes from Prior Versions of the SAP

SAP V2.0: Sigma Tau Pharmaceuticals' name was updated to Leadiant Biosciences. [REDACTED] as the named statistical services vendor on STP206-002 [REDACTED]

SAP V3.0: Incorporates changes due to Protocol Amendment 2. See History of Protocol Changes, dated 08JUL2018 and redlined Protocol, version 3.0 for full description of changes.

6 BASELINE, EFFICACY AND SAFETY EVALUATIONS

6.1 Schedule of Evaluations

The assessments to be conducted at each scheduled visit are displayed in the following table.

AE=adverse event; BP=blood pressure; BPD=bronchopulmonary dysplasia; HR=heart rate; IVH=intraventricular hemorrhage; NEC=necrotizing enterocolitis; NICU=neonatal intensive care unit; ROP=retinopathy of prematurity; RR=respiratory rate; SpO₂= pulse oximetry.

- a. If available.
- b. To be performed daily in NICU per standard NICU procedures, adverse findings to be recorded as AEs or complications of prematurity.
- c. To be performed at per standard NICU protocols for assessment of ROP.
- d. Cranial ultrasound will be performed at between 5 and 7 days of age and at 28 (± 3 days) of age for assessment of IVH; if neonate is discharged from the hospital prior to 28 days of age or the procedure is not clinically indicated, the cranial ultrasound may be deferred.
- e. Assessments for BDP will be performed per NICU standard protocols by the attending physician and is defined as oxygen requirements at 36 weeks post conceptional age to keep oxygen saturation levels above 90%.
- f. Day 7 only.

Table 2 Schedule of Events Post Dosing Period

Protocol STP206-002 Schedule of Events Post Dosing Period					
Procedure	Week 1 ±2 days	1 Month (Day 30 -35)	3 Months (Day 85 – 99)	6 Months (Day 181 – 195)	Early Withdrawal Prior to 6 Months
Physical Examination	x	x	x	x	x
Vital Signs (Temp, BP, HR, RR)	x	x	x	x	x
Growth Assessment	x	x	x	x	x
Adverse Event Assessment	x	x	x	x	x
Concomitant Medications Evaluation (Infant)	x	x	x	x	x

6.2 Time Point Algorithms

6.2.1 Relative Day

The date of first dose of study treatment will be considered as study day 1, and the day before the first dose of study treatment will be relative day -1. Study days will be calculated as follows only when the full assessment date is known (i.e., partial dates will have missing study days).

For days on or after the first dose of study treatment:

Date of Assessment – Date of First Dose of study treatment + 1.

For days before the first dose of study treatment:

Date of Assessment – Date of First Dose of study treatment.

6.2.2 Windows

The time schedule described in the protocol for each scheduled activity will be followed as closely as possible. The time windows noted in Table 4 will be used for analysis purposes.

Table 4: Analysis Visit Windows for Dosing Period and Post Dosing

Nominal Visit during dosing period (Target Day)	Protocol Window	Study Day Analysis Visit Window Range
Baseline	Collected at birth, screening, or/and Week 1 Day 1 before study dosing	Sample assessment date < Date of First Dose of study treatment
1 Hour ^a	1 Hour + 10 minutes	1 Hour + 30 minutes

Nominal Visit during dosing period (Target Day)	Protocol Window	Study Day Analysis Visit Window Range
2 Hour ^a	2 Hour \pm 10 minutes	2 Hour \pm 30 minutes
3 Hour ^a	3 Hour \pm 10 minutes	3 Hour \pm 30 minutes
4 Hour ^a	4 Hour \pm 10 minutes	4 Hour \pm 30 minutes
8 Hour ^a	8 Hour \pm 10 minutes	8 Hour \pm 30 minutes
12 Hour ^a	12 Hour \pm 10 minutes	12 Hour \pm 30 minutes
16 Hour ^a	16 Hour \pm 10 minutes	16 Hour \pm 30 minutes
20 Hour ^a	20 Hour \pm 10 minutes	20 Hour \pm 30 minutes
24 Hour ^a	24 Hour \pm 10 minutes	24 Hour \pm 30 minutes
Week 1 (Day 1-4) ^b	day 1, day 2, day 3, day 4	day 1, day 2, day 3, day 4
Week 1 (Day 5-7) ^{b,c,d}	day 5, day 6, day 7	day 5, day 6, day 7
Week 2 (Day 14) ^{b,d}	13 to 16 days	13 to 17 days
Week 3 (Day 21) ^b	20 to 22 days	18 to 24 days
Week 4 (Day 28) ^{b,d}	25 to 32 days	25 to 32 days
Week 5 (Day 35) ^b	34 to 36 days	33 to 38 days
Week 6 (Day 42) ^{b,d}	41 to 42 days	39 to 45 days
Week 7 (Day 49) ^b	48 to 50 days	46 to 52 days
Week 8 (Day 56) ^{b,d}	55 to 57 days	53 to 59 days
Week 9 (Day 63) ^b	62 to 64 days	60 to 66 days
Week 10 (Day 70) ^{b,d}	69 to 71 days	67 to 73 days
Week 11 (Day 77) ^b	76 to 78 days	74 to 80 days
End of Dosing or Hospital Discharge ^{b,d} (for Growth Assessment, and fecal sample only)	Not specified	For fecal sample: sample assessment date - last dose date \geq 0 For growth assessment: 0 \leq sample assessment date - last dose date \leq 5 days
Nominal Visit during Post Dosing		Post Study Day Analysis Visit Window Range^e
Post Dosing 1 Week ^d	5 to 9 days	6day \leq (assessment date – expected last dose date+1) \leq 13 days
Post Dosing 1 Month ^d	30 to 35 days	21 days \leq (assessment date – expected last dose date+1) \leq 35 days
Post Dosing 3 Month ^d	85 to 99 days	85 \leq (assessment date – expected last dose date+1) \leq 99 days

Nominal Visit during dosing period (Target Day)	Protocol Window	Study Day Analysis Visit Window Range
Post Dosing 6 Month ^d	181 to 195 days	181 <= (assessment date – expected last dose date+1) <= 195 days
Post Dosing 18 Month/End ^d	Not specified	520 <= (assessment date – expected last dose date+1) <= 576 days
Withdrawal Prior to Post Dosing 6 Month ^d	Not specified	assessment date >= date of withdrawal and (assessment date – expected last dose date+1) <= 181 days
Withdrawal between Post Dosing 6 and 18 Month ^d	Not specified	assessment date >= date of withdrawal and 196 days < (assessment date – expected last dose date+1) < 520 days

- a- Windows for vital sign measurements and physical examinations.
- b- Window for fecal sample.
- c- Window for IVH measurement.
- d- Windows for growth assessment (note that Post Dosing 18 Month data will only be presented in listings).
- e- Windows for Post Dosing may be adjusted to account for patients that terminated dosing early. For example, if a subject early terminates dosing at Week 10 but was expected to complete dosing at Week 11, then the Post Dosing window will be adjusted to reflect planned time point after expected dosing completion.

If a subject has more than 1 assessment occurring in the same visit window, the data from the visit closest to the scheduled study day will be used for summaries. If two assessments have the same distance from the scheduled study day, the assessment after the scheduled study day will be used for the analyses.

If multiple assessments occur as Baseline (screening or Day 1 prior to dosing), then the last assessment before the first study dose will be used for the analyses.

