
Study Endpoints:
 
Primary Endpoint:
 
 
The incidence and severity of adverse events (AEs), serious adverse events (SAEs), and changes in clinical parameters from baseline in STP206-treated subjects compared to control subjects from baseline through 30 days after the last dose of blinded study treatment
 
 
Secondary Endpoints:
 
 
The incidence and the severity of AEs and SAEs in STP206-treated subjects compared to control subjects from baseline through six months after the last dose of blinded study treatment
 
The incidence of clinical events (NEC, sepsis/bacteremia, feeding intolerance, death, morbidity/complications of prematurity) in STP206-treated subjects compared to control subjects from baseline through hospital discharge
 
The assessment of the fecal shedding of STP206 organisms in STP206-treated subjects compared to its baseline and to control subjects through the last dose of blinded study treatment
 
The assessment of the changes in routine clinical parameters in STP206-treated subjects compared to control subjects at baseline through the last dose of blinded study treatment
 
The assessment of the progression of standard neonatal growth parameters in STP206 treated subjects compared to control subjects through the 6-month postdosing visit.
 
 
Exploratory Endpoints:
 
 
The incidence of suspected NEC (Stage I NEC) in STP206-treated subjects compared to control subjects through hospital discharge
 
The incidence of suspected sepsis in STP206-treated subjects compared to control subjects through hospital discharge
 
The incidence of antibiotic usage in STP206-treated subjects compared to control subjects through hospital discharge
 

 
		
Study Design and Methodology:		

		IND No.: BB 14,046
Protocol No.: STP206-002	Development Phase: I	Indication: Necrotizing Enterocolitis
Protocol Title: A Phase Ib Randomized, Placebo Controlled Study of the Safety and Efficacy of Once Daily Dosing of STP206 in Premature Very Low Birth Weight and Extremely Low Birth Weight Neonates		

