## **10.8. Study Medication Administration and Compliance**

### 10.8.1. Dosage and Administration

Dosing of blinded study drug will be initiated within 4 days (i.e., 96 hours) after birth. Dosing is intended to consist of a single daily bolus dose administered as part of a scheduled feeding. However, in neonates who are volume restricted, the total daily dose may be divided and given twice daily (BID) or three times daily (TID) until full amount can be tolerated in one dose. In neonates where the dose volume is less than the maximum volume tolerated, dosing may be supplemented with regular feeding. In neonates receiving continuous feeds, the feed will be interrupted for dose administration and then immediately restarted. The date, time and volume of each dose administration will be recorded.

In neonates who are still on tube feeds, the dose will be given by feeding tube prior to feeding. If dosing at the time of feeding is not possible, the dose may be given and then the line flushed with sterile water to assure delivery of the full dose. In larger neonates who feed orally by breast or bottle for all feeds and do not have a feeding tube in place, the dose will be fed directly into the mouth before a feed using a syringe intended for oral drug administration. In the event the dose is spit up, the neonate will not be re-dosed. Regurgitation of the dose will be noted in the source document and the case report form.

Prior to administration, subject identification will be verified against the labeled syringes to ensure that the correct IP is given.

The times of product reconstitution and dose administration will be recorded. Reconstituted components of STP206 should be administered within 2 hours following reconstitution.

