#### 11.3.2.1. Week 1: Day 1 (Start of Dosing)

Subjects who pass screening evaluations and are eligible for enrollment will be randomized to study treatment.

Prior to dosing, the following study procedures will be performed:

- Physical Examination
- Vital Signs

- Growth Assessment
- Changes in concomitant medications since the screening assessment
- Fecal sample: all fecal samples produced will be collected daily through Day 4 and then once weekly afterward.

Blinded study treatment will be administered to the neonate and the time of administration recorded. Following the initial dose administration, the neonate will be observed continuously by a member of the study staff over the first 60 minutes following administration of study drug and following procedures will be conducted:

- Vital signs every hour ( $\pm 10$  minutes) for 4 hours, then every 4 hours ( $\pm 30$  minutes) through 24 hours following dose administration
- Physical Examination at 3 hours ( $\pm 1$  hour) following dose administration

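### SAP Table 4 conflicts with the SAP's own text or the protocol on baseline, the 3-hour examination and the post-dosing day count; only descriptive by-time-point tables are affected

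*SAP*

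**What the plan says.** SAP 6.2.2 makes the Table 4 windows the ones used for analysis. Three sets of entries matter.

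**Baseline.** The analysis cell reads "Sample assessment date < Date of First Dose of study treatment". The neighbouring cell of that row lists Week 1 Day 1 before dosing among the baseline times. The text under the table also counts Day 1 pre-dose values as baseline and, where there are several, says that "the last assessment before the first study dose will be used for the analyses". SAP 6.2.1 states: "The date of first dose of study treatment will be considered as study day 1". Protocol 11.3.2.1 introduces its Day 1 list with "Prior to dosing, the following study procedures will be performed"; the list includes the physical examination, vital signs, growth and a fecal sample.

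**3-hour physical examination.** Protocol 11.3.2.1 schedules it at 3 hours ±1 hour after the first dose. Table 4 gives the 3 Hour row ±30 minutes, and footnote a applies the hourly rows to examinations as well as vital signs. SAP 8.7.4 summarises examinations at pre-dose and 3 hours only.

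**Post-dosing growth.** Protocol 11.3.3 sets the visits at 1 week ±2 days and at 30-35, 85-99 and 181-195 days following completion of dosing. Table 4 applies the limits 6-13, 21-35, 85-99 and 181-195 to a count that adds 1. The 6-month cell, for example, is "181 <= (assessment date – expected last dose date+1) <= 195 days". The later withdrawal row requires "196 days < (assessment date – expected last dose date+1) < 520 days". Footnote d assigns these rows to growth assessments.

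**The concern.** A programmer will code the cells of Table 4, so a wrong cell matters even where nearby text shows a different intent.

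The baseline cell sets the reference value for several tables. The primary endpoint includes "changes in clinical parameters from baseline in STP206-treated subjects compared to control subjects", and SAP 8.7.4 summarises vital signs as change from baseline, with pre-dose rows for examinations, growth and fecal organisms. If the cell were followed, Day 1 pre-dose values would give way to older screening values. An infant screened and first dosed on one date would have no baseline vital signs or examination. Pre-exposure stools would enter an on-treatment summary.

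The examination window can leave a protocol-compliant examination outside the only post-dose examination time point that is tabulated. The growth windows can drop a compliant visit at the edge of its range.

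The groups are small. With 12 infants per study group randomised 2:1, 12 × 2/3 = 8 receive STP206 and 12 × 1/3 = 4 receive control, so one misplaced value is visible in a table by stratum and dose.

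**Working it through.** **1. Baseline.** For a Day 1 pre-dose value, assessment date minus first-dose date = 0.
- Table 4 cell: the difference must be below 0, so the value fails.
- SAP 6.2.1: study day = 0 + 1 = 1, so a Day 1 pre-dose stool meets the Week 1 (Day 1-4) window.
- Neighbouring cell, text below the table, and protocol 11.3.2.1: the value is baseline.

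Replacing < by ≤ on dates would not help, because values taken after the dose on Day 1 also have a difference of 0. The rule needs clock time or a pre-dose label. The cell's opening word does not confine it to stool: the end-of-dosing row uses the same term for growth.

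**2. Examination.**
- Protocol: 180 ± 60 minutes = 120 to 240, a span of 120 minutes.
- Table 4, 3 Hour row: 180 ± 30 minutes = 150 to 210, a span of 60 minutes.
- Covered: 60/120 of the permitted interval.

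An examination at 2 h 15 min (135 minutes) is compliant but falls in the 2 Hour row (90-150). One at 3 h 45 min (225 minutes) falls in the 4 Hour row (210-270). SAP 8.7.4 has no examination summary at either time.

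**3. Post-dosing count.** Table 4's protocol-window column reproduces the protocol: 7 ± 2 = 5-9, then 30-35, 85-99 and 181-195. Let d be days after the last dose, with dosing completed as expected. The SAP count is d + 1.

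| Visit | Protocol days | SAP limits on d + 1 | d accepted | Compliant days kept |
|---|---|---|---|---|
| 1 week | 5-9 | 6-13 | 5-12 | 5/5 |
| 1 month | 30-35 | 21-35 | 20-34 | 5/6 (35 lost) |
| 3 months | 85-99 | 85-99 | 84-98 | 14/15 (99 lost, 84 admitted) |
| 6 months | 181-195 | 181-195 | 180-194 | 14/15 (195 lost, 180 admitted) |

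If the protocol days are instead numbered with the last dose as day 1, they can be compared with the SAP limits directly. The 1-, 3- and 6-month rows then keep 6/6, 15/15 and 15/15, but 1 week keeps 4/5 (day 5 lost). If the formula is read as subtracting the day after the last dose, the count is d − 1, and days 5 and 6 at 1 week, 85 and 181 are lost. No reading makes all four rows consistent.

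Day 195 gives count 196, which fits no row: the 6 Month row stops at 195 and the later withdrawal row starts above 196.

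**Check of the corrections**, with d as days after the last dose:
- Drop +1, 1-week limits 5-13, other limits unchanged: accepted 5-13, 21-35, 85-99, 181-195. Kept 5/5, 6/6, 15/15, 15/15; days 84 and 180 excluded.
- Keep +1, limits 6-13, 21-36, 86-100, 182-196: accepted 5-12, 20-35, 85-99, 181-195. Kept 5/5, 6/6, 15/15, 15/15; days 84 and 180 excluded.
- Keep +1 and raise only the upper limits to 36, 100 and 196: all compliant days are kept, but d = 84 and d = 180 still enter.

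**The case against.** **Baseline.** The text below Table 4 states the intended rule plainly, so this is a wording error in one cell and not a gap in the plan. That stands. It does not remove the conflict, because the SAP then holds two incompatible rules and says the table's windows will be used. A reader might infer that some infants will lack a baseline, or that baselines will be up to four days old because "Dosing of blinded study drug will be initiated within 4 days (i.e., 96 hours) after birth". The documents do not support either as a finding. Both arise only if the cell is followed over the text. The 96 hours is a ceiling on the time from birth to first dose, and the number of infants screened and dosed on one date is not given.

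**Examination.** The protocol schedules one timed examination after the first dose, so its nominal visit is clear, and the SAP does not say that one outside ±30 minutes is discarded. Under protocol 10.3.1, adverse findings from later NICU examinations are recorded as adverse events or complications of prematurity. A reader might infer that half the examinations would be lost. That does not follow, because 60/120 is a share of permitted time, and the timing of actual examinations is unknown. What stands is that the stated window disagrees with the protocol and no rule covers the remainder.

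**Post-dosing count.** The visit schedules label these visits by day number and SAP 6.2.1 numbers the first-dose date as day 1, so numbering the last dose as day 1 is a fair reading. It removes the loss at 1, 3 and 6 months. The wording of protocol 11.3.3 favours counting days after the last dose, and the alternative breaks the 1-week row instead. The gap at count 196 is not a fault in itself: the windows are not contiguous, and data beyond Month 6 go to listings.

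**Anchor date.** A reader might also infer that counting from the expected last dose date is an error. Footnote e discloses and explains it, it is arguable for growth, which depends on age, and nothing above needs it.

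**Conclusion.** Table 4 is wrong as written in three places and should be corrected before the tables are programmed. The baseline cell and the examination window are the two that matter; the growth count is minor.

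- Baseline: coded literally, all Day 1 pre-dose values are excluded. The intended rule is already in the SAP.
- Examination: the analysis window covers 60 of the 120 minutes the protocol permits.
- Growth: one edge day is lost at each of 1, 3 and 6 months, or one day at 1 week, depending on how the last dose is numbered. The first result assumes dosing ended on the expected date.

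The number of infants affected is unknown for all three. The effect is confined to descriptive by-time-point tables. Adverse-event tables and listings do not use these windows, and all comparisons are exploratory. The documents do not support a stronger claim that the safety conclusions are at risk.

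**What to change.** 1. **Baseline.** Replace the cell with: last value with date and time before the date and time of first dose. Start the Day 1-4 fecal window after the first dose. The protocol records times for Day 1 vital signs (10.3.2), stool collection (10.4) and each dose (10.8.1). Where only a date is held, use the pre-dose label of the assessment.
2. **Examination.** Give the 3-hour physical examination its own 3 h ±1 h row, and limit footnote a to vital signs.
3. **Growth.** Preferred: drop the +1, set the 1-week lower limit to 5 and keep the other limits. Align the withdrawal rows, with the later one starting at ≥196 instead of >196 and the earlier one ending at 180 so that day 181 belongs to one row. If the +1 is kept, shift both limits at 3 and 6 months (86-100 and 182-196) and raise the 1-month upper limit to 36. The present withdrawal limits (≤181 and >196) then fit as they stand. Say in one sentence how the last dose is numbered.

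The cost is a revision of Table 4 and its footnotes and reprogramming of the visit windows. No new data are needed.
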